## Overview

Protocol I6T-MC-AMBV, “Relative Bioavailability of a Mirikizumab Test Formulation Compared to the Reference Formulation in Healthy Subjects”, has been amended. The new protocol is indicated by Amendment (a) and will be used to conduct the study in place of any preceding version of the protocol.

The overall changes and rationale for the changes made to this protocol are as follows:

- Expanded exclusion criterion [10] to exclude employees of any third-party organization to be involved in the study
- The language in exclusion criteria [23], [24], and [25] is modified to clarify subjects with positive HIV antibodies, hepatitis C antibodies, hepatitis B surface antigen or hepatitis B core antibodies will be excluded
- Included timeframe for subjects who have had household contact with a person with active TB to be excluded from study
- Throughout the protocol changes have been made to reflect the fact that the study will be conducted at a single study site. These changes are not presented in the revised section below.

## Revised Protocol Sections

**Note:** All deletions have been identified by ~~strike-throughs~~.  
All additions have been identified by the use of underscore.

### 6.2 Exclusion Criteria

Subjects will be excluded from study enrollment if they meet any of the following criteria at screening and/or Day -1:

- [9] are site staff directly affiliated with this study and their immediate families.  
Immediate family is defined as a spouse, biological or legal guardian, child, or sibling
- [10] are Lilly ~~or Covance~~ employees or are employees of a third-party organization involved in the study
- [23] show ~~evidence of HIV infection and/or~~ positive HIV antibodies
- [24] show ~~evidence of hepatitis C and/or~~ positive hepatitis C antibody
- [25] show ~~evidence of hepatitis B and/or~~ positive hepatitis B surface antigen or hepatitis B core antibody

#### 9.4.5.1 Tuberculosis Testing

Subjects who have had household contact with a person with active TB within 1 year of screening must be excluded

Leo Document ID = 9dc24504-fe1f-4a57-8b01-c4098bb8ebf9

Approver: PPD

Approval Date & Time: 17-Aug-2020 14:09:30 GMT

Signature meaning: Approved

Approver: PPD

Approval Date & Time: 17-Aug-2020 15:49:23 GMT

Signature meaning: Approved

## 2. ABBREVIATIONS

Abbreviations pertain to the Statistical Analysis Plan (SAP) only (not the tables, figures and listings [TFLs]).

%AUC( $t_{\text{last}}-\infty$ )	Percentage of AUC( $0-\infty$ ) extrapolated
ADA	Anti-drug antibody
AE	Adverse event
AUC	Area under the concentration versus time curve
AUC( $0-\infty$ )	Area under the concentration versus time curve from time zero to infinity
AUC( $0-t_{\text{last}}$ )	Area under the concentration versus time curve from time zero to time $t$ , where $t$ is the last time point with a measurable concentration
BQL	Below the quantifiable lower limit of the assay
CI	Confidence interval
CL/F	Apparent total body clearance of drug calculated after extra-vascular administration
$C_{\text{last}}$	Last quantifiable drug concentration
$C_{\text{max}}$	Maximum observed drug concentration
CRU	Clinical Research Unit
CSR	Clinical Study Report
ECG	Electrocardiogram
ICH	International Conference on Harmonisation
MedDRA	Medical Dictionary for Regulatory Activities
PFS	Pre-filled syringe
PK	Pharmacokinetic
SAE	Serious adverse event
SAP	Statistical Analysis Plan
SC	Subcutaneous
SD	Standard deviation
$t_{1/2}$	Half-life associated with the terminal rate constant ( $\lambda_z$ ) in non-compartmental analysis
TE ADA	Treatment-emergent antidrug antibody
TEAE	Treatment-emergent adverse event
TFLs	Tables, Figures, and Listings

---

$t_{max}$	Time of maximum observed drug concentration
ULN	Upper limit of normal
VAS	Visual analog scale
$V_{ss/F}$	Apparent volume of distribution at steady state after extravascular administration
$V_z/F$	Apparent volume of distribution during the terminal phase after extra-vascular administration
WHO	World Health Organization

### 3. INTRODUCTION

This SAP has been developed after review of the Clinical Study Protocol (final version dated 13 December 2019).

This SAP describes the planned analysis of the safety, tolerability and pharmacokinetic (PK) data from this study. A detailed description of the planned TFLs to be presented in the clinical study report (CSR) is provided in the accompanying TFL shell document.

The intent of this document is to provide guidance for the statistical and PK analyses of data. In general, the analyses are based on information from the protocol, unless they have been modified by agreement with Eli Lilly and Company. A limited amount of information concerning this study (e.g., objectives, study design) is given to help the reader's interpretation. When the SAP and TFL shells are agreed upon and finalized, they will serve as the template for this study's CSR.

This SAP supersedes the statistical considerations identified in the protocol; where considerations are substantially different, they will be so identified. If additional analyses are required to supplement the planned analyses described in this SAP, they may be performed and will be identified in the CSR. Any substantial deviations from this SAP will be agreed upon with Eli Lilly and Company and identified in the CSR. Any minor deviations from the TFLs may not be documented in the CSR.

This SAP is written with consideration of the recommendations outlined in the International Conference on Harmonisation (ICH) E9 Guideline entitled Guidance for Industry: Statistical Principles for Clinical Trials and the ICH E3 Guideline entitled Guidance for Industry: Structure and Content of Clinical Study Reports.

### 4. STUDY OBJECTIVES AND ENDPOINTS

Objectives	Endpoints
Primary 

To evaluate the relative bioavailability of a single 200-mg subcutaneous (SC) dose (2 x 1-mL pre-filled syringe [PFS] injections) of Mirikizumab Test Formulation compared to the Reference Formulation

	

Maximum observed drug concentration (<math>C_{max}</math>), area under the concentration versus time curve from time zero to infinity [<math>AUC(0-\infty)</math>], and area under the concentration versus time curve from time zero to time <math>t</math>, where <math>t</math> is the last timepoint with a measurable concentration [<math>AUC(0-t_{last})</math>]

Secondary 

To evaluate the safety and tolerability of a single 200-mg SC dose (2 x 1-mL PFS injections) of Mirikizumab Test Formulation compared to the Reference

	

Treatment-emergent adverse events (TEAEs), and serious adverse events (SAEs)

Formulation	
CCI [REDACTED] [REDACTED] [REDACTED]	[REDACTED] [REDACTED] [REDACTED]

## 5. STUDY DESIGN

Study AMBV is a Phase 1, subject-blind, investigator-blind, 2-arm, randomized, single-dose, parallel-design study in healthy subjects.

All subjects will be screened within 28 days prior to enrollment. Eligible subjects will be admitted to the clinical research unit (CRU) on Day -1 and randomized

- 1:1 to 2 treatment formulations and
- within each treatment formulation, 1:1:1 to 3 injection sites (arm, thigh, or abdomen)

using a computer-generated allocation code. On Day 1, subjects will receive a 2 x 1-mL (200 mg mirikizumab) SC dose of 1 of the following treatments according to the randomization schedule:

- 200 mg Mirikizumab Reference Formulation (100 mg/mL), 2 x 1-mL PFS
- 200 mg Mirikizumab Test Formulation (100 mg/mL), 2 x 1-mL PFS

The maximum total dose of mirikizumab a subject will receive is 200 mg.

Subjects may be allowed to leave the CRU after completing the 4-hour safety assessments on Day 1, at the investigator's discretion, and will return for PK and immunogenicity sampling and safety assessments at predefined times up to 12 weeks postdose. Subjects will be monitored for safety between outpatient visits by way of telephone assessment. Subjects will participate in the study for up to 12 weeks after last dose.

Safety and tolerability will be assessed through clinical laboratory tests, vital sign measurements, recording of adverse events (AEs), physical examination, and immunogenicity. At prospectively defined time points, injection-related assessments will be made including a VAS pain score.

## 6. TREATMENTS

The following is a list of the study treatment abbreviations that will be used in the TFLs.

Study Treatment Name	Injection Site	Abbreviation	Treatment order in TFL
200 mg Mirikizumab Reference Formulation (100 mg/mL) 2 x 1-mL PFS	Arm	Reference (Arm)	1
	Thigh	Reference (Thigh)	2
	Abdomen	Reference (Abdomen)	3
200 mg Mirikizumab Test Formulation (100 mg/mL) 2 x 1-mL PFS	Arm	Test (Arm)	4
	Thigh	Test (Thigh)	5
	Abdomen	Test (Abdomen)	6

## 7. SAMPLE SIZE JUSTIFICATION

Up to 60 subjects may be enrolled to ensure that 48 subjects (24 subjects per treatment formulation with approximately 8 subjects per treatment formulation and injection site [arm, thigh, or abdomen]) complete the study.

Based on previous trials, it is expected that the coefficient of variation for area under the concentration versus time curve (AUC) and  $C_{max}$  to be approximately 40%. A sample size of 48 completed subjects (24 subjects per treatment formulation) will provide >90% probability that the limits of the 90% confidence interval (CI) for the ratio of geometric means will be within 24% of the estimate.

Subjects who are randomized but not administered any treatment formulation may be replaced to ensure that 48 subjects (24 per treatment formulation) complete the study.

## 8. DEFINITION OF ANALYSIS POPULATIONS

The “Safety” population will consist of all enrolled subjects who received at least one dose of mirikizumab, regardless of whether they complete all protocol requirements.

The “Pharmacokinetic” population will consist of all subjects who received at least one dose of mirikizumab and have evaluable PK data.

All protocol deviations that occur during the study will be considered for their severity/impact and will be taken into consideration when subjects are assigned to analysis populations.

## 9. STATISTICAL METHODOLOGY

### 9.1 General

Data listings will be provided for all data that is databased. Summary statistics and statistical analysis will only be presented for data where detailed in this SAP. For continuous data, summary statistics will include the arithmetic mean, arithmetic standard deviation (SD), median, min, max and N; for log-normal data (e.g. the PK parameters: AUCs and  $C_{max}$ ) the geometric

mean and geometric coefficient of variation will also be presented. For categorical data, frequency count and percentages will be presented. Data listings will be provided for all subjects up to the point of withdrawal, with any subjects excluded from the relevant population highlighted. Summary statistics and statistical analyses will generally only be performed for subjects included in the relevant analysis population. For the calculation of summary statistics and statistical analysis, unrounded data will be used.

Mean change from baseline is the mean of all individual subjects' change from baseline values. Each individual change from baseline will be calculated by subtracting the individual subject's baseline value from the value at the timepoint. The individual subject's change from baseline values will be used to calculate the mean change from baseline using a SAS procedure such as Proc Univariate.

Data analysis will be performed using SAS® Version 9.4 or greater.

## **9.2 Demographics and Subject Disposition**

Subject disposition will be listed. The demographic variables age, sex, race, ethnicity, country of enrolment, site ID, body weight, height and body mass index will be summarized by treatment formulation and injection site and listed. All other demographic variables will be listed only.

## **9.3 Pharmacokinetic Assessment**

### **9.3.1 Pharmacokinetic Analysis**

PK parameter estimates will be determined using non-compartmental procedures in validated software program (Phoenix WinNonlin Version 8.1 or later).

Serum concentrations of mirikizumab will be used to determine the following PK parameters, when possible:

[figure not shown]
Parameter	Units	Definition
AUC(0-t last )	day* $\mu$ g/mL	area under the concentration versus time curve from time zero to time t, where t is the last time point with a measurable concentration
AUC(0-∞)	day* $\mu$ g/mL	area under the concentration versus time curve from time zero to infinity
%AUC(t last -∞)	%	percentage of AUC(0-∞) extrapolated
C max	$\mu$ g/mL	maximum observed drug concentration
t max	day	time of maximum observed drug concentration
t 1/2	day	half-life associated with the terminal rate constant ( $\lambda_z$ ) in non-compartmental analysis
CL/F	L/day	apparent total body clearance of drug calculated after extra-vascular administration
V Z /F	L	apparent volume of distribution during the terminal phase after extra-vascular administration
V ss /F	L	apparent volume of distribution at steady state after extra-vascular administration

Additional PK parameters may be calculated, as appropriate.

PK parameters may also be normalized by body weight in the event that there are differences in body weight between the cohorts.

The software and version used for the final analyses will be specified in the clinical study report. Any exceptions or special handling of data will be clearly documented within the final study report.

CCI

## General PK Parameter Rules

- Actual sampling times will be used in the final analyses of individual PK parameters, except for non-bolus pre-dose sampling times which will be set to zero.
- Cmax and the time of maximum observed drug concentration (tmax) will be reported from observed values. If Cmax occurs at more than one time point, tmax will be assigned to the first occurrence of Cmax.
- AUC parameters will be calculated using a combination of the linear and logarithmic trapezoidal methods (linear-log trapezoidal rule). The linear trapezoidal method will be applied up to tmax and then the logarithmic trapezoidal method will be used after tmax. The minimum requirement for the calculation of AUC will be the inclusion of at least three consecutive concentrations above the lower limit of quantification, with at least one of these concentrations following Cmax.

- AUC(0-∞) values where the percentage of the total area extrapolated is more than 20% will be flagged. Any AUC(0-∞) value excluded from summary statistics will be noted in the footnote of the summary table.
- Half-life ( $t_{1/2}$ ) will be calculated, when appropriate, based on the apparent terminal log-linear portion of the concentration-time curve. The start of the terminal elimination phase for each subject will be defined by visual inspection and generally will be the first point at which there is no systematic deviation from the log-linear decline in serum concentrations. Half-life will only be calculated when a reliable estimate for this parameter can be obtained comprising of at least 3 data points. If  $t_{1/2}$  is estimated over a time window of less than 2 half-lives, the values will be flagged in the data listings. Any  $t_{1/2}$  value excluded from summary statistics will be documented in the footnote of the summary table.
- A uniform weighting scheme will be used in the regression analysis of the terminal log-linear portion of the concentration-time curve.
- The parameters based on observed last quantifiable drug concentration ( $C_{last}$ ) will be reported.

### Individual PK Parameter Rules

- Only quantifiable concentrations will be used to calculate PK parameters with the exception of special handling of certain concentrations below the quantifiable lower limit of the assay (BQL). Serum concentrations reported as BQL will be set to a value of zero when all of the following conditions are met:
  - The compound is non-endogenous.
  - The samples are from the initial dose period for a subject or from a subsequent dose period following a suitable wash-out period.
  - The time points occur before the first quantifiable concentration.
- All other BQL concentrations that do not meet the above criteria will be set to missing.
- Also, where two or more consecutive concentrations are BQL towards the end of a profile, the profile will be deemed to have terminated and therefore any further quantifiable concentrations will be set to missing for the calculation of the PK parameters unless it is considered to be a true characteristic of the profile of the drug.

### Individual Concentration vs. Time Profiles

- Individual concentrations will be plotted utilizing actual sampling times.
- The terminal point selections will be indicated on a semi-logarithmic plot.

### Average Concentration vs. Time Profiles

- The average concentration profiles will be graphed using scheduled (nominal) sampling times.
- The average concentration profiles will be graphed using arithmetic average concentrations.
- The pre-dose average concentration for single-dose data from non-endogenous compounds will be set to zero. Otherwise, only quantifiable concentrations will be used to calculate average concentrations.
- Concentrations at a sampling time exceeding the sampling time window specified in the protocol, or  $\pm 10\%$ , will be excluded from the average concentration profiles.
- Concentrations excluded from the mean calculation will be documented in the final study report.
- A concentration average will be plotted for a given sampling time only if 2/3 of the individual data at the time point have quantifiable measurements that are within the sampling time window specified in the protocol or  $\pm 10\%$ . An average concentration estimated with less than 2/3 but more than 3 data points may be displayed on the mean concentration plot if determined to be appropriate and will be documented within the final study report.

### Treatment of Outliers during Pharmacokinetic Analysis

Application of this procedure to all PK analyses is not a requirement. Rather, this procedure provides justification for exclusion of data when scientifically appropriate. This procedure describes the methodology for identifying an individual value as an outlier for potential exclusion but does not require that the value be excluded from analysis. The following methodology will not be used to exclude complete profiles from analysis.

#### Data within an Individual Profile

A value within an individual profile may be excluded from analysis if any of the following criteria are met:

- For PK profiles during single dosing of non-endogenous compounds, the concentration in a pre-dose sample is quantifiable.
- For any questionable datum that does not satisfy the above criteria, the profile will be evaluated, and results reported with and without the suspected datum.

#### Data between Individual Profiles

1. If  $n < 6$ , then the dataset is too small to conduct a reliable range test. Data will be analyzed with and without the atypical value, and both sets of results will be reported.

2. If  $n \geq 6$ , then an objective outlier test will be used to compare the atypical value to other values included in that calculation:

- a. Transform all values in the calculation to the logarithmic domain.
- b. Find the most extreme value from the arithmetic mean of the log transformed values and exclude that value from the dataset.
- c. Calculate the lower and upper bounds of the range defined by the arithmetic mean  $\pm 3*SD$  of the remaining log-transformed values.
- d. If the extreme value is within the range of arithmetic mean  $\pm 3*SD$ , then it is not an outlier and will be retained in the dataset.
- e. If the extreme value is outside the range of arithmetic mean  $\pm 3*SD$ , then it is an outlier and will be excluded from analysis.

If the remaining dataset contains another atypical datum suspected to be an outlier and  $n \geq 6$  following the exclusion, then repeat step 2 above. This evaluation may be repeated as many times as necessary, excluding only one suspected outlier in each iteration, until all data remaining in the dataset fall within the range of arithmetic mean  $\pm 3*SD$  of the log-transformed values.

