#### Reporting of Excluded Values

Individual values excluded as outliers will be documented in the final report. Approval of the final report will connote approval of the exclusion.

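### SAP 9.3.1 lets a PK value be dropped on a 3-SD test alone when n is 6 or more, and no visible text requires the result with that value kept in (minor)

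*SAP*

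**What the plan says.** The rule is in SAP 9.3.1, under Treatment of Outliers during Pharmacokinetic Analysis and the subsections that follow it.

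- **Opening paragraph.** Applying the procedure is not compulsory: "this procedure provides justification for exclusion of data when scientifically appropriate", and the method "does not require that the value be excluded from analysis". It also sets a limit: "The following methodology will not be used to exclude complete profiles from analysis". What counts as scientifically appropriate is not defined.
- **Data within an Individual Profile.** For a questionable point that does not meet the stated exclusion criterion, the profile is evaluated and "results reported with and without the suspected datum".
- **Data between Individual Profiles, n<6.** "Data will be analyzed with and without the atypical value, and both sets of results will be reported".
- **Data between Individual Profiles, n≥6.** An objective test is used to "compare the atypical value to other values included in that calculation". Values are logged, the most extreme is set aside, and the mean ± 3 SD of the remainder is formed. If the value is outside that range, "then it is an outlier and will be excluded from analysis". The step may be repeated, one value at a time, while at least six values remain.
- **Reporting of Excluded Values.** "Individual values excluded as outliers will be documented in the final report". Approval of the report counts as approval of the exclusion.

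SAP 9.3.2 fits log Cmax, AUC(0-tlast) and AUC(0-∞) on formulation and injection-site location and reports the Test/Reference ratio with a 90% CI. It does not mention the outlier procedure. SAP 8 and Protocol 10.3 base the PK analysis on all dosed subjects with evaluable PK data.

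**The concern.** The SAP asks for both sets of results in two of its three outlier situations. The exception is n≥6, and the planned sets are 8 per formulation and site, 24 per formulation and 48 overall, so n≥6 is the branch that would apply. Under it a value can be removed without a dosing, sampling or assay reason, and the ratio with the value kept in need not be shown.

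Step e and the opening paragraph also disagree on whether exclusion follows automatically. In addition, the phrase that sets the comparison group does not identify it. SAP 9.3.2 contains several calculations that could be meant: the 48-subject model, Test against Reference at each site, site comparisons within each formulation, and summaries by formulation and site.

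The trial's deliverable is a ratio and its 90% CI, and the sample size was justified by the precision of that CI. A discretionary exclusion that shifts the ratio and narrows the CI should not be the only result on the page.

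**Working it through.** **Inputs.** CV about 40%, 24 per formulation, about 8 per formulation and site, and the precision target of 24% with probability above 90% (SAP 7; Protocol 10.1). Model: formulation + location (SAP 9.3.2). Outlier rule: SAP 9.3.1 as written. Assumptions: log-normal data, no true outlier, independent subjects, and every flagged value excluded. The last makes the figures upper bounds.

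**1. The plan's own precision figure.** σ = √ln(1 + 0.40²) = 0.385. The 90% CI half-width at S = σ, with 46 df, is 1.679 × 0.385 × √(2/24) = 0.187 on the log scale; the limit is ln 1.24 = 0.215. P(half-width ≤ 0.215) = P(χ²₄₆ ≤ 46 × (0.2151/0.1867)² = 61.1) = 0.932. With the model's 44 df it is 0.927. Both exceed 90%, so the stated figure reproduces.

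**2. How often the rule flags a valid value (first pass).** The deviation of one value from the mean of the other n−1, divided by their SD × √(1 + 1/(n−1)), follows a t distribution with n−2 df. The value is therefore flagged when |t| > 3√((n−1)/n). Multiplying the tail probability by n gives a close upper bound per set.

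| Set | Cut-off | Two-sided tail | × n | Whole trial |
|---|---|---|---|---|
| 48 pooled | 2.969 | 0.00474 | 0.227 | 0.227 |
| 24 per formulation | 2.937 | 0.00763 | 0.183 | 1 − (1 − 0.183)² = 0.333 |
| 8 per cell | 2.806 | 0.0309 | 0.247 | 1 − (1 − 0.247)⁶ = 0.818 |

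**3. Effect on the 90% CI.** The full iterated rule was simulated with the SAP 9.3.2 model at a true ratio of 1, in runs of 6,000 to 20,000 trials that agreed within about a percentage point.

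| Comparison set | Trials losing a valid value | 90% CI coverage |
|---|---|---|
| No exclusion | 0% | about 90% |
| 48 pooled | about 22% | about 89.8% |
| 24 per formulation | about 33% | about 87.5% |
| 8 per cell | about 82% | about 85% |

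At a true ratio of 1.25 the pooled rule gives coverage of about 89%, with a log-ratio bias of about −0.01, because the formulation difference then forms part of the pooled spread.

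**4. Size when a value is dropped (pooled).** The mean absolute shift in the log ratio is about 0.05 (90th percentile 0.066), and the CI half-width is about 0.90 of the full-data one. By hand, removing one value 3σ out in an arm of 24 moves the ratio by exp(3 × 0.385/24) = 1.049. Averaged over all trials, most of which lose nothing, the shift is about 1.1%.

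**5. Sensitivity (assumed settings).** If half of the flags are acted on, 12% of trials lose a value pooled (coverage 90.1%) and 19% by formulation (88.9%). With a quarter, the figures are 6.5% (89.8%) and 10% (89.3%). If log values follow a t distribution with 5 df, with every flag acted on, the loss rates are 65%, 72% and 93% for sets of 48, 24 and 8, and coverage is 90.6%, 86.9% and 85.6%.

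**The case against.** Most of the case on the other side stands, and it keeps the point minor.

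- **Automatic deletion.** A reader of step e alone might infer that the SAP mandates it. The opening paragraph introduces the procedure and makes exclusion optional. The test is also aimed at a value already thought atypical, not at the extreme value of every dataset, so the rates above are ceilings.
- **Reach to the primary ratio.** The rule directly follows the rules for average concentration profiles and is absent from SAP 9.3.2. It may be meant only for concentrations or summary statistics. Against that, step e refers to exclusion from analysis, while the General PK Parameter Rules refer to summary statistics when they mean those. The text does not settle it.
- **Loss of accuracy.** On the pooled reading, which is the natural one for the 48-subject model, a reader might infer a damaged primary analysis. That is not so: RMSE is 0.109 against 0.111 on full data at ratio 1, and coverage is near nominal.
- **Hidden exclusions.** They would not be hidden. SAP 9.1 lists all data, SAP 9.3.1 documents special handling, and excluded values are reported. The all-data ratio could be recomputed from the listings. But this does not oblige anyone to present it.
- **Requiring a documented error.** This is a trade-off, not a correction. If one Test value were wrong by being 5-fold too low (assumed), keeping it gives a log-ratio bias of −0.067 and RMSE of 0.129, against −0.004 and 0.111 under the pooled rule.
- **Different subjects behind Cmax and the AUCs.** This is not a defect of the rule. SAP 9.3.1 already derives parameters only when possible and allows individual AUC(0-∞) values to be left out of summaries.

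Some text in SAP 9.3.1 and Protocol 10.3 is blacked out, so the statement is that no visible text requires both results.

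**Conclusion.** The point holds and is minor. For n≥6 a PK value may be dropped on the 3-SD test alone, the comparison set is not identified, and no visible text requires the ratio with the value retained, although the SAP asks for exactly that in its other two outlier situations.

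The choice of set matters more than the rule itself. Pooling all 48 leaves coverage close to 90%; testing by formulation or by cell lowers it to about 87.5% or 85% if every flag is acted on. Where a value is dropped under pooling, the reported ratio moves about 5% and its CI narrows about 10%.

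These sizes rest on the SAP's CV of 40%, log-normal data and full use of the rule, and they apply only if the rule reaches the SAP 9.3.2 model. No acceptance bound is set in the visible text, so the effect is on the estimate and its stated precision, not on a pass/fail decision.

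**What to change.** In SAP 9.3.1 and 9.3.2:

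1. For every n, whenever the outlier test leads to an exclusion that affects Cmax, AUC(0-tlast) or AUC(0-∞) in the 9.3.2 model, report the Test/Reference ratio and 90% CI both with and without the value.
2. Name the comparison set. For the primary ratio, do not run the test separately by formulation or by formulation-by-site cell.
3. Reword step e so that a flagged value *may* be excluded, in line with the opening paragraph.
4. If the procedure is meant only for concentrations or summary statistics, say so; the primary ratio is then untouched.

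The cost is a few lines of SAP text and one extra table, produced only if a value is excluded. Limiting exclusions to documented dosing, sampling or assay errors is optional, given the trade-off in bias and RMSE.
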